10.1.8 Study and Site Start and Closure

First Act of Recruitment

The study start date is the date on which the clinical study will be open for recruitment of participants.

The first act of recruitment is the first site activated and will be the study start date.

Study/Site Termination

The Sponsor or designee reserves the right to close the study site or terminate the study at any time for any reason at the sole discretion of the Sponsor. Study sites will be closed upon study completion. A study site is considered closed when all required documents and study supplies have been collected and a study-site closure visit has been performed.

The Investigator may initiate study-site closure at any time, provided there is reasonable cause and sufficient notice is given in advance of the intended termination.

Reasons for the early closure of a study site by the Sponsor or Investigator may include but are not limited to:

For study termination:

• Discontinuation of further study product development

For site termination:

• Failure of the Investigator to comply with the protocol, the requirements of the IRB/IEC or local health authorities, the Sponsor's procedures, or GCP guidelines

- Inadequate or no recruitment (evaluated after a reasonable amount of time) of participants by the Investigator
- Total number of participants included earlier than expected

If the study is prematurely terminated or suspended, the Sponsor shall promptly inform the Investigators, the IECs/IRBs, the regulatory authorities, and any contract research organization(s) used in the study of the reason for termination or suspension, as specified by the applicable regulatory requirements. The Investigator shall promptly inform the participant and should assure appropriate participant therapy and/or follow-up.

10.1.9 Publication Policy

- The results of this study may be published or presented at scientific meetings. The Investigator will submit any proposed publication or presentation along with the respective scientific journal or presentation forum at least 30 days before submission of the publication or presentation. The Investigator will comply with Dermavant Sciences, Inc. request to delete references to its confidential information (other than the study results) in any paper or presentation and agrees to withhold publication or presentation for an additional 60 days in order to obtain patent protection if deemed necessary. This allows the Sponsor to protect proprietary information and to provide comments.
- After conclusion of the study and without prior written approval from Dermavant Sciences, Inc., Investigators in this study may communicate, orally present, or publish in scientific journals or other scholarly media only after the following conditions have been met:
 - The results of the study in their entirety have been publicly disclosed by or with the consent of Dermavant Sciences, Inc., in an abstract, manuscript, or presentation form; OR
 - The study has been completed at all study sites for at least 5 years.
- No such communication, presentation, or publication will include Dermavant Sciences, Inc. confidential information.
- The Sponsor will comply with the requirements for publication of study results. In accordance with standard editorial and ethical practice, the Sponsor will generally support publication of multicenter studies only in their entirety and not as individual site data. In this case, a coordinating Investigator will be designated by mutual agreement.
- Authorship will be determined by mutual agreement and in line with International Committee of Medical Journal Editors authorship requirements.

DMVT-505 (tapinarof) Dermavant Sciences, Inc. IND 104601 Clinical Study Protocol

10.2 Appendix 2: Clinical Laboratory Tests

No clinical laboratory tests will be performed in this study.

10.3 Appendix 3: AEs and SAEs: Definitions and Procedures for Recording, Evaluating, Follow-up, and Reporting

10.3.1 Definition of AE

AE Definition

- An AE is any untoward medical occurrence in a clinical study participant, temporally associated with the use of study product, whether or not considered related to the study product.
- NOTE: An AE can therefore be any unfavorable and unintended sign (including an abnormal laboratory finding), symptom, or disease (new or exacerbated) temporally associated with the use of study product.

Definition of Unsolicited and Solicited AE

- An unsolicited AE is an AE that was not solicited using a participant diary and that is communicated by a participant who has signed the informed consent. Unsolicited AEs include serious and nonserious AEs.
- Potential unsolicited AEs may be medically attended (i.e., symptoms or illnesses requiring a hospitalization, emergency room visit, or visit to/by a healthcare provider). The participant will be instructed to contact the site as soon as possible to report medically attended event(s), as well as any events that, though not medically attended, are of participant concern. Detailed information about reported unsolicited AEs will be collected by qualified site personnel and documented in the participant's records.
- Unsolicited AEs that are not medically attended nor perceived as a concern by the participant will be collected during an interview with the participant and by review of available medical records at the next visit.
- Solicited AEs are predefined local and systemic events for which the participant is specifically questioned, and which are noted by the participant in their diary.

Events Meeting the AE Definition

- Any abnormal laboratory test results (hematology, clinical chemistry, or urinalysis) or other safety
 assessments (e.g., ECG, radiological scans, vital signs measurements), including those that worsen
 from baseline, considered clinically significant in the medical and scientific judgment of the
 Investigator (i.e., not related to progression of underlying disease, or more severe than expected for
 the participant's condition)
- Exacerbation of a chronic or intermittent pre-existing condition including either an increase in frequency and/or intensity of the condition
- New condition detected or diagnosed after study product administration even though it may have been present before the start of the study
- Signs, symptoms, or the clinical sequelae of a suspected drug-drug interaction
- Signs, symptoms, or the clinical sequelae of a suspected overdose of either study product or a concomitant medication. Overdose per se will not be reported as an AE/SAE unless it is an intentional overdose taken with possible suicidal/self-harming intent. Such overdoses should be reported regardless of sequelae.
- Lack of efficacy or failure of expected pharmacological action per se will not be reported as an AE or SAE. Such instances will be captured in the efficacy assessments. However, the signs, symptoms, and/or clinical sequelae resulting from lack of efficacy will be reported as AE or SAE if they fulfill the definition of an AE or SAE.

Events not Meeting the AE Definition

- Any abnormal laboratory findings or other abnormal safety assessments that are associated with the underlying disease, unless judged by the Investigator to be more severe than expected for the participant's condition
- The disease/disorder being studied or expected progression, signs, or symptoms of the disease/disorder being studied, unless more severe than expected for the participant's condition
- Medical or surgical procedure (e.g., endoscopy, appendectomy): The condition that leads to the procedure is the AE.
- Situations in which an untoward medical occurrence did not occur (social and/or convenience admission to a hospital)
- Anticipated day-to-day fluctuations of pre-existing disease(s) or condition(s) present or detected at the start of the study that do not worsen

10.3.2 Definition of SAE

An SAE is defined as any untoward medical occurrence that, at any dose, meets one or more of the criteria listed:

a. Results in death

b. Is life threatening

The term life threatening in the definition of serious refers to an event in which the participant was at risk of death at the time of the event. It does not refer to an event, which hypothetically might have caused death, if it were more severe.

c. Requires inpatient hospitalization or prolongation of existing hospitalization

- In general, hospitalization signifies that the participant has been admitted (usually involving at least an overnight stay) at the hospital or emergency ward for observation and/or treatment that would not have been appropriate in the physician's office or outpatient setting. Complications that occur during hospitalization are AEs. If a complication prolongs hospitalization or fulfills any other serious criteria, the event is serious. When in doubt as to whether hospitalization occurred or was necessary, the AE should be considered serious.
- Hospitalization for elective treatment of a pre-existing condition that did not worsen from baseline is not considered an AE.

d. Results in persistent or significant disability/incapacity

- The term disability means a substantial disruption of a person's ability to conduct normal life functions.
- This definition is not intended to include experiences of relatively minor medical significance such as uncomplicated headache, nausea, vomiting, diarrhea, influenza, and accidental trauma (e.g., sprained ankle) that may interfere with or prevent everyday life functions but do not constitute a substantial disruption.
- e. Is a congenital anomaly/birth defect
- f. Is a suspected transmission of any infectious agent via an authorized medicinal product

g. Other situations:

• Medical or scientific judgment should be exercised by the Investigator in deciding whether SAE reporting is appropriate in other situations such as important medical events that that may not be immediately life-threatening or result in death or hospitalization but may jeopardize the participant

DMVT-505 (tapinarof) Dermavant Sciences, Inc.

or may require medical or surgical intervention to prevent one of the other outcomes listed in the above definition. These events should usually be considered serious.

o Examples of such events include invasive or malignant cancers, intensive treatment in an emergency room or at home for allergic bronchospasm, blood dyscrasias, convulsions not resulting in hospitalization, or development of intervention dependency or intervention abuse.

10.3.3 Recording and Follow-Up of AE and/or SAE

AE and SAE Recording

- When an AE/SAE occurs, it is the responsibility of the Investigator to review all documentation (e.g., hospital progress notes, laboratory reports, and diagnostics reports) related to the event.
- The Investigator will then record all relevant AE/SAE information.
- It is not acceptable for the Investigator to send photocopies of the participant's medical records to the Sponsor in lieu of completion of the required form.
- There may be instances when copies of medical records for certain cases are requested by regulatory authorities. In this case, all participant identifiers, with the exception of the participant number, will be redacted on the copies of the medical records before submission to regulatory authorities.
- The Investigator will attempt to establish a diagnosis of the event based on signs, symptoms, and/or other clinical information. Whenever possible, the diagnosis (not the individual signs/symptoms) will be documented as the AE/SAE.

Assessment of Severity

The Investigator will make an assessment of severity for each AE and SAE reported during the study according to the National Cancer Institute CTCAE, v. 5.0, 2017. For terms not specified with the CTCAE, the criteria in Table 4 should be used to determine the grade severity.

Table 4: Criteria for Determining the Grade/Severity of Adverse Event Terms Not Specified by the National Cancer Institute CTCAE

Grade	Criteria		
1	Mild; asymptomatic or mild symptoms, clinical or diagnostic observations only; intervention not indicated		
2	Moderate; minimal, local, or noninvasive intervention indicated; limiting age-appropriate instrumental activities of daily living ^a		
3	Severe or medically significant but not immediately life-threatening; hospitalization or prolongation of hospitalization indicated; disabling; limiting self-care activities of daily living ^b		
4	Life-threatening consequences; urgent intervention indicated		
5	Death related to adverse event		

a. Instrumental activities of daily living refer to preparing meals, shopping for groceries or clothes, using the telephone, managing money, etc.

CTCAE = Common Terminology Criteria for Adverse Events.

b. Self-care activities of daily living refer to bathing, dressing and undressing, feeding self, using the toilet, taking medications, and not bedridden.

Assessment of Causality

- The Investigator is obligated to assess the relationship between study product and each occurrence of each AE/SAE. The Investigator will use clinical judgment to determine the relationship.
- A reasonable possibility of a relationship conveys that there are facts, evidence, and/or arguments to suggest a causal relationship, rather than a relationship cannot be ruled out.
- Alternative causes, such as underlying disease(s), concomitant therapy, and other risk factors, as well as the temporal relationship of the event to study product administration, will be considered and investigated.
- For causality assessment, the Investigator will also consult the IB and/or product information, for marketed products.
- The Investigator must review and provide an assessment of causality for each AE/SAE and document this in the medical notes. There may be situations in which an SAE has occurred, and the Investigator has minimal information to include in the initial report to the Sponsor or designee. However, it is very important that the Investigator always make an assessment of causality for every event before the initial transmission of the SAE data to the Sponsor or designee.
- The Investigator may change their opinion of causality in light of follow-up information and send an SAE follow-up report with the updated causality assessment.
- The causality assessment is one of the criteria used when determining regulatory reporting requirements.

Follow-up of AEs and SAEs

- The Investigator is obligated to perform or arrange for the conduct of supplemental measurements and/or evaluations as medically indicated or as requested by the Sponsor or designee to elucidate the nature and/or causality of the AE or SAE as fully as possible. This may include additional laboratory tests or investigations, histopathological examinations, or consultation with other health care professionals.
- If a participant dies during participation in the study or during a recognized follow-up period, the Investigator will provide the Sponsor with a copy of any postmortem findings including histopathology, if applicable.
- New or updated information will be recorded in the originally submitted documents.
- The Investigator will submit any updated SAE data to the Sponsor or designee within 24 hours of receipt of the information.

10.3.4 Reporting of SAEs

SAE Reporting to Sponsor via an Electronic Data Collection Tool

- The primary mechanism for reporting an SAE to the Sponsor or designee will be the electronic data collection tool.
- If the electronic system is unavailable, then the site will use the paper SAE data collection tool (see next section) to report the event within 24 hours.
- The site will enter the SAE data into the electronic system as soon as it becomes available.
- After the study is completed at a given site, the electronic data collection tool will be taken offline to prevent the entry of new data or changes to existing data.
- If a site receives a report of a new SAE from a study participant or receives updated data on a previously reported SAE after the electronic data collection tool has been taken offline, then the

site can report this information on a paper SAE form (see next section) or to the Sponsor or designee by telephone.

• Contacts for SAE reporting can be found in Study Reference Manual.

SAE Reporting to Sponsor or Designee via Paper Data Collection Tool

- Facsimile transmission of the SAE paper data collection tool is the preferred method to transmit this information to the Sponsor or designee or the SAE coordinator.
- Initial notification via telephone does not replace the need for the Investigator to complete and sign the SAE data collection tool within the designated reporting timeframes.
- Contacts for SAE reporting can be found in the Study Reference Manual.

10.4 Appendix 4: Contraceptive and Barrier Guidance

10.4.1 Definitions

Woman of Childbearing Potential (WOCBP)

Women in the following categories are considered WOCBP (fertile):

- 1. Following menarche
- 2. From the time of menarche until becoming postmenopausal unless permanently sterile (see below)
 - A postmenopausal state is defined as no menses for 12 months without an alternative medical cause.
 - A high FSH level in the postmenopausal range may be used to confirm a postmenopausal state in women not using hormonal contraception or HRT. However, in the absence of 12 months of amenorrhea, confirmation with more than one FSH measurement is required.
 - Females on HRT and whose menopausal status is in doubt will be required to use one of the nonestrogen hormonal highly effective contraception methods if they wish to continue their HRT during the study. Otherwise, they must discontinue HRT to allow confirmation of postmenopausal status before study enrollment.
 - Permanent sterilization methods (for the purpose of this study) include:
 - Documented hysterectomy
 - o Documented bilateral salpingectomy
 - o Documented bilateral oophorectomy
 - For individuals with permanent infertility due to an alternate medical cause other than the above (e.g., Mullerian agenesis, androgen insensitivity, gonadal dysgenesis), Investigator discretion should be applied to determining study entry.

Note: Documentation can come from the site personnel's review of the participant's medical records, medical examination, or medical history interview.

• If fertility is unclear (e.g., amenorrhea in adolescents or athletes) and a menstrual cycle cannot be confirmed before first dose of study product, additional evaluation should be considered.

Woman of Nonchildbearing Potential (WONCBP)

Women in the following categories are considered WONCBP:

- 1. Premenopausal female with permanent infertility due to one of the following:
 - a. Documented hysterectomy
 - b. Documented bilateral salpingectomy
 - c. Documented bilateral oophorectomy
 - d. For individuals with permanent infertility due to an alternate medical cause other than the above (e.g., Mullerian agenesis, androgen insensitivity, gonadal dysgenesis), Investigator discretion should be applied to determining study entry.

Note: Documentation can come from the site personnel's review of the participant's medical records, medical examination, or medical history interview.

2. Postmenopausal female

- a. A postmenopausal state is defined as no menses for 12 months without an alternative medical cause.
 - i. A high FSH level in the postmenopausal range may be used to confirm a postmenopausal state in women not using hormonal contraception or HRT. However, in the absence of 12 months of amenorrhea, confirmation with more than one FSH measurement is required.
 - ii. Females on HRT and whose menopausal status is in doubt must discontinue HRT to allow confirmation of postmenopausal status before study enrollment.

10.4.2 Contraception Guidance

CONTRACEPTIVES^a ALLOWED DURING THE STUDY INCLUDE:

Highly Effective Methods^b **That Have Low User Dependency** *Failure rate of* $\leq 1\%$ *per year when used consistently and correctly.*

- Implantable progestogen-only hormone contraception associated with inhibition of ovulation^c
- Intrauterine device (IUD)
- Intrauterine hormone-releasing system (IUS)c
- Bilateral tubal occlusion
- Azoospermi^c partner (vasectomized or due to a medical cause)

Azoospermia is a highly effective contraceptive method provided that the partner is the sole sexual partner of the woman of childbearing potential and the absence of sperm has been confirmed. If not, an additional highly effective method of contraception should be used. Spermatogenesis cycle is approximately 90 days.

Note: Documentation of azoospermia for a male participant can come from the site personnel's review of the participant's medical records, medical examination, or medical history interview.

Highly Effective Methods^b That Are User Dependent Failure rate of < 1% per year when used consistently and correctly.

Combined (estrogen- and progestogen-containing) hormonal contraception associated with inhibition of ovulation^c

- oral
- intravaginal
- transdermal
- injectable

Progestogen-only hormone contraception associated with inhibition of ovulation^c

- oral
- injectable

Sexual abstinence

Sexual abstinence is considered a highly effective method only if defined as refraining from heterosexual intercourse during the entire period of risk associated with the study product. The reliability of sexual abstinence needs to be evaluated in relation to the duration of the study and the preferred and usual lifestyle of the participant.

Effective Methods^d That Are Not Considered Highly Effective Failure rate of $\geq 1\%$ per year when used consistently and correctly.

- Progestogen-only oral hormonal contraception where inhibition of ovulation is not the primary mode of action
- Male or female condom with or without spermicide
- Cervical cap, diaphragm, or sponge with spermicide
- A combination of male condom with either cervical cap, diaphragm, or sponge with spermicide (double-barrier methods)^c
- a) Contraceptive use by men or women should be consistent with local regulations regarding the use of contraceptive methods for those participating in clinical studies.
- b) Failure rate of $\leq 1\%$ per year when used consistently and correctly. Typical use failure rates differ from those when used consistently and correctly.
- c.) If locally required, in accordance with Clinical Trial Facilitation Group (CTFG) guidelines, acceptable contraceptive methods are limited to those which inhibit ovulation as the primary mode of action.
- d) Considered effective, but not highly effective—failure rate of $\geq 1\%$ per year.

Note: Periodic abstinence (calendar, symptothermal, postovulation methods), withdrawal (coitus interruptus), spermicides only, and lactational amenorrhea method (LAM) are not acceptable methods of contraception. Male condom and female condom should not be used together (due to risk of failure from friction).

10.5 Appendix 5: Physician Global Assessment of Intertriginous Areas

In this study, this PGA should be used only to assess plaque PSO in intertriginous areas (iPGA).

Each assessment should be made as a visual "average" of the severity of all treated intertriginous areas at the time of the assessment. Following the Baseline visit, assessments will be made without reference to Baseline state or any other previous scores.

Scoring should not be influenced by extent of lesions, participant symptoms, or impact on participant's quality of life.

Score/Grade		Description
0	Clear	No signs of psoriasis; postinflammatory hyperpigmentation may be present
1	Almost clear	No thickening; normal to pink coloration; no to minimal focal scaling
2	Mild	Just detectable to mild thickening; pink to light red coloration; predominantly fine scaling
3	Moderate	Clearly distinguishable to moderate thickening; dull to bright red, clearly distinguishable erythema; moderate scaling
4	Severe	Severe thickening with hard edges; bright to deep dark red coloration; severe/coarse scaling covering almost all or all lesions

Source: Langley RGB, Feldman SR, Nyirady J, van de Kerkhof P, Papavassilis C. The 5-point Investigator's Global Assessment (IGA) Scale: A modified tool for evaluating plaque psoriasis severity in clinical trials. J Dermatolog Treat. 2015;26(1):23-31.

[figure not shown]
Dermavant Sciences, Inc.	Clinical Study Protoco

[figure not shown]
IND 104601

DMVT-505 (tapinarof)

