5.1 Inclusion Criteria

Participants are eligible to be included in the study only if all of the following criteria apply:

Age

1. Participant must be 18 years of age or older, at the time of signing the informed consent.

Type of Participant and Disease Characteristics

- 2. Participants with clinical diagnosis of plaque PSO, including lesion(s) in intertriginous area(s) and stable disease in intertriginous areas for at least 3 months prior to the study
- 3. An iPGA score of 2 (mild), 3 (moderate), or 4 (severe) at screening and baseline.

Sex and Contraceptive/Barrier Requirements

Contraceptive use by men and women should be consistent with local regulations regarding the methods of contraception for those participating in clinical studies.

4. Female participants:

A female participant is eligible to participate if she is not pregnant or breastfeeding, and one of the following conditions applies:

- Is a WONCBP as defined in Appendix 4 Contraceptive and Barrier Guidance OR
- Is a WOCBP and using an acceptable contraceptive method as described in Appendix 4 Contraceptive and Barrier Guidance during the treatment period, until after the last dose of study product. The Investigator should evaluate the potential for contraceptive method failure (e.g., noncompliance, recently initiated) in relationship to the first dose of study product).
 - A WOCBP must have a negative urine pregnancy test before the first dose of study product, see Section 8.3.1 Pregnancy Testing.
 - The Investigator is responsible for review of medical history, menstrual history, and recent sexual activity to decrease the risk for inclusion of a woman with an early undetected pregnancy.

Informed Consent

5. Capable of giving signed informed consent as described in Appendix 1 which includes compliance with the requirements and restrictions listed in the ICF and in this protocol; written informed consent must be obtained prior to any study related procedures.

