6.9 Prior and Concomitant Therapy

Any medication or vaccine, including over the counter or prescription medicines, recreational drugs, vitamins, and/or herbal supplements, as well as non-medicated emollients, that the participant is utilizing at the time of consent or receives during the study must be recorded along with:

- Reason for use
- Dates of administration including start and end dates
- Dosage information including dose and frequency

The medical monitor should be contacted if there are any questions regarding concomitant or prior therapy.

Concomitant medications for medical treatment of other conditions are allowed, under the condition that the dosage and administration of these treatments are not planned to change from the Baseline visit to the completion of the study or discontinuation, and that the medication is not a prohibited medication as described in Section 5.2.

In the event of skin infection, topical antibacterial agents can be applied to the infected area; however, study product must not be applied to the area until the skin infection is healed.

Participants may use non-medicated shampoos (must not contain corticosteroids, vitamin D analogs, salicylic acid, or coal tar). Non-medicated emollients may be used outside of the intertriginous areas; emollients should not be applied to intertriginous skin. The same emollient should be used throughout participation in the study.

7 Discontinuation of Study Intervention and Participant Discontinuation/Withdrawal

Discontinuation of specific sites or of the study as a whole are detailed in Appendix 1.

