7.1.1 Temporary Discontinuation

Some dermatological reactions have been observed following treatment with VTAMA (tapinarof) cream, 1% (see Section 2.3.1). After cessation of exposure, dermatological reactions generally subside spontaneously or with topical treatments.

In this study, treatment of plaque PSO in intertriginous regions with study product may be interrupted for dermatological reactions. If treatment is interrupted due to a safety issue, the Medical Monitor will be contacted, and the event documented in the eCRF.

See Section 10.3.5 for further information on the management of follicular events.

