8.2.1.1 Physician Global Assessment of Intertriginous Areas

The PGA is a clinical tool for assessing the current state/severity of a participant's PSO at a given time point. It is a static 5-point morphological assessment of overall disease severity, as determined by the Investigator, using the clinical characteristics of erythema, scaling, and plaque thickness/elevation as guidelines; higher PGA scores represent more severe disease (see Appendix 5).

In this study, the PGA should be used only to assess plaque PSO in intertriginous areas (iPGA).

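### Does the word *treated* in the iPGA definition let a fold with product withheld leave the score and create a false responder?

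*Protocol*

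**What the plan says.** Protocol Appendix 5 (Section 10.5) asks the rater for a visual average "of the severity of all treated intertriginous areas at the time of the assessment". It adds: "Following the Baseline visit, assessments will be made without reference to Baseline state or any other previous scores". Section 8.2.1.1 describes the scale: "It is a static 5-point morphological assessment of overall disease severity". That section restricts the score to intertriginous areas, without the word *treated*, and sends the reader to Appendix 5 for the grades.

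Two other sections allow product to be withheld. On skin infection, Section 6.9 says that "study product must not be applied to the area until the skin infection is healed". Section 7.1.1 says that "treatment of plaque PSO in intertriginous regions with study product may be interrupted for dermatological reactions". Section 7.1.2 allows treatment to resume once a reaction has subsided.

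Eligibility under Section 5.1 requires "An iPGA score of 2 (mild), 3 (moderate), or 4 (severe) at screening and baseline". SAP Section 6.4 takes as baseline the last value before first dose. Section 8.1.4 and Table 2 of the protocol have participants treat all intertriginous lesions; Section 8.1.4 includes those that are new and those that have improved or cleared.

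The missing-data and efficacy sections of the SAP (5.6 and 7.2) do not mention a fold from which product is withheld.

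**The concern.** Read quickly, the Appendix 5 sentence seems to limit the score to folds receiving product on the day of the visit. Because the protocol itself takes product away from some folds, a post-baseline event could then change what is measured. If the withheld fold was the one that had not improved, the average would fall when it left, and the bias would run towards response. With no control arm, nothing would offset it.

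Two further features add to the unease. No area has been treated at Screening or Baseline, so the same sentence seems to leave the baseline score without a defined area. Section 8.2.1.1 also omits the qualifier, which looks like a second definition of the same score. If both points held, Baseline and Week 12 could cover different folds, and raters could differ in what they average.

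**Working it through.** The plan gives no figure to reproduce: N = 30 rests on clinical considerations (Protocol 9.5) and no testing is planned (9.1). The check therefore has two parts, the wording and the size.

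**Wording**

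1. *What the time phrase modifies.* Sections 4.2 and 8.2.1.1 describe the PGA as a static measure of the current state of disease. In that setting the phrase about the time of assessment belongs with severity: grade what is there now. The sentence does not say that product must currently be applied.
2. *Test of the strict reading.* The iPGA must be scored at Screening and Baseline, before any dose. If *treated* meant now receiving product, the set of areas would be empty at both visits and nobody could qualify. That reading cannot be what was meant for a sentence that governs each assessment.
3. *What the documents supply instead.* Every intertriginous lesion is to be treated, including new and cleared ones. The areas under study treatment are therefore all involved folds.
4. *Whether there are two definitions.* Section 8.2.1.1 points to Appendix 5, and Appendix 5 opens with nearly the same restriction to intertriginous areas. Both separate skin folds from the rest of the body. Neither sets up a rival list of folds.
5. *When a single fold loses product.* Only the infection rule in Section 6.9 is expressly specific to an area. Section 7.1.1 speaks of intertriginous regions in general. If all of them were interrupted, the strict reading would give no score at all, not a false responder.

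**Size, if the strict reading were applied**

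Assumptions: *m* equally weighted folds, all at grade *b* at Baseline. At Week 12 one withheld fold is still at *b* and the others are at *s*. The mean is rounded half up. Response means a score of 0 or 1 and a fall of at least 2 grades.

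Mean over all folds = [*b* + (*m* − 1)*s*] / *m*. Without the withheld fold the score is *s*.

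| *b* | *m* | *s* | All folds | Withheld fold dropped |
|---|---|---|---|---|
| 3 | 2 | 1 | (3 + 1)/2 = 2, non-responder | 1, responder |
| 3 | 4 | 1 | (3 + 3)/4 = 1.5, scored 2, non-responder | 1, responder |
| 4 | 5 | 1 | (4 + 4)/5 = 1.6, scored 2, non-responder | 1, responder |
| 3 | 3 | 0 | (3 + 0)/3 = 1, responder | 0, responder |

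Reclassification is thus possible but not automatic. Each case moves the rate by 1/30 = 3.3 points.

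Taking a true count of 15/30 (assumed) and exact Clopper-Pearson limits:

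| False responders | Rate | 95% CI |
|---|---|---|
| 0 | 50.0% | 31.3 to 68.7 |
| 1 | 53.3% | 34.3 to 71.7 |
| 2 | 56.7% | 37.4 to 74.5 |
| 3 | 60.0% | 40.6 to 77.3 |

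The interval with no false responders is 68.7 − 31.3 = 37.4 points wide.

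The documents do not say how often a fold would be withheld at Week 12. If 2%, 5% or 10% of participants were affected (assumed), the expected number is 30 × 0.02 = 0.6, 30 × 0.05 = 1.5 or 30 × 0.10 = 3.0. The chance of at least one, 1 − (1 − *q*)^30, is 46%, 79% or 96%. These are participants with a withheld fold; the number reclassified would be the same or smaller.

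**The case for a change.** The strongest case for acting is that the Baseline argument shows only that the sentence cannot be applied literally at every visit. It does not say what a rater should do at Week 12 with a fold that is off product. *Treated* is undefined, no visible text keeps such a fold in the score, and raters are told not to look back to Baseline. The diary is described as recording the time of application, not the folds covered, so a wrong choice could be hard to undo. A one-sentence clarification would be cheap.

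The gap in the definition is real, and so is the arithmetic possibility. The rest is weaker:

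- Only a fold withheld at the Week 12 visit affects the observed-case primary result. Earlier withholding could touch time to response, or the supportive LOCF summary if Week 12 is missing.
- Infected lesions are excluded at entry (Section 5.2), and withholding for infection lasts only until healing.
- It is not established that a withheld fold is one where psoriasis is doing badly. The scale grades the thickening, colour and scaling of psoriasis, not infection or a reaction as such.
- The average is a visual judgement, not a mean of equally weighted folds.
- Section 8.2.1 requires trained raters and, as far as possible, the same rater for each participant.
- Such cases would leave a trace. Safety interruptions are documented in the eCRF (Section 7.1.1), and concomitant medication, which would include topical antibacterials, is recorded with dates (Section 6.9).
- Making the Baseline list of folds the reference for later scoring would need care, because Appendix 5 has raters score without reference to Baseline.

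**Conclusion.** No change to the plan is needed. The feared rule, scoring only folds that are on product that day, is not what Appendix 5 most naturally says, and it fails at the plan's own Screening and Baseline visits. Read with the application instructions, the scoring set is every involved intertriginous area. What is left is an unstated detail for a fold that is off product at the visit. A trained rater asked for the current severity of intertriginous disease would reasonably keep that fold in view.

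If a rater did drop one, the cost is at most 3.3 points of 30 per participant, against an interval about 37 points wide at an assumed 15/30, in a descriptive study with no test to distort. The number of such participants is unknown. Any total, such as 6.7 points for two (2/30) or 13.3 points for four (4/30), assumes both that they occur and that every one is reclassified. The conclusion rests on the visible text; the Schedule of Activities and the rater-training content could not be examined.
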